## **7.5. Safety Analysis**

The safety evaluations include AEs, concomitant medication, clinical laboratory assessments. Safety analysis will be assessed by induction and consolidation for the safety population.

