## 12 Statistical Considerations

### 12.1 Study Design & Sample Size Considerations

This is a randomized, open-label Phase II study comparing gilteritinib to midostaurin in patients receiving standard induction therapy with cytarabine and daunorubicin in FLT3 mutated AML. Patients will be stratified according to FLT3-TKD vs. FLT3-ITD mutation. Patients with FLT3-ITD mutation will undergo further stratification with NPM1 mutation status (positive vs. negative) and signal ratio (high [ $\geq 0.5$ ] vs. low [ $<0.5$ ] of FLT3 Wild Type). Patients will be randomized to receive standard induction treatment (cytarabine and daunorubicin) with either gilteritinib or midostaurin. If achieving CR or CRi, these patients will go on to receive standard consolidation treatment of high-dose cytarabine with the study drug received during induction (gilteritinib or midostaurin). Patients may proceed to allogeneic transplant after induction or after 0-4 cycles of chemotherapy consolidation. The primary objective of this study is to assess the FLT3 mutation negative CRc (includes CR and CRi) rate of patients who receive gilteritinib compared to those who receive midostaurin in addition to standard therapy with cytarabine and daunorubicin after induction. FLT3 mutation negativity is evaluated by PCR at the end of induction.

Based on a retrospective study performed at John-Hopkins, we assume with the control arm of cytarabine, daunorubicin and midostaurin, the FLT3 mutation negative CRc rate after induction is 40%. With 170 eligible patients with allocation ratio of 1:1 to the two arms, the study will have 80% power to detect an improvement of 20% in the FLT3 mutation negative CRc rate in the gilteritinib arm (i.e., from 40% to 60%) at the one-sided significance level of 0.05 based on Fisher's exact test. Accounting for 5% ineligibility, we will need a total of 179 patients.

Assume 7 FLT3 mutated patients will be accrued each month, the accrual of the study will be completed in 2.1 years.

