##### **4.4.1. Study Treatment Schedule**

There are 2 treatment arms. The treatment with midostaurin is the control arm, denoted as Arm B. The treatment with gilteritinib is the investigation medication arm, denoted as Arm A.

Arm A treatment: cytarabine + daunorubicin +

Gilteritinib. Arm B treatment: cytarabine +

daunorubicin + Midostaurin. Induction: There are 1- 2

cycle of therapy in induction.

Consolidation: There are 0 - 4 cycles of therapy in Consolidation.

Consolidation cycle 1, patients who achieve a CR or CRi and have no residual significant toxicities from the induction course are eligible for consolidation therapy. In general, consolidation therapy should start within 1 month of CR/CRi.

Consolidation Cycle 2-4, Patients must have maintained remission during the consolidation cycles. Patients who do not begin consolidation Cycle 2-4 within 30 days of recovery from previous cycle are ineligible for further protocol therapy.

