### **7.4.1. Safety Population**

Safety population is used for safety analysis. The safety population is defined as all patients treated with at least one dose of study medication during the study. All safety data collected up to the end of the study are included in the safety analysis.

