### **7.5.4. Concomitant Medications and Procedure**

The use of concomitant medications and procedure will be recorded on the CRFs. The concomitant medications will be coded to a World Health Organization Drug Dictionary (WHO-DD) term (Version WHODRUG Version - March 2016).

The use of concomitant medications and procedures will be summarized by arm and overall, for the safety population for induction and consolidation separately. In each of these summary tables, the number and percentage of patients taking each medication will be presented by ATC Classification.

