### **7.5.6. Adverse Event**

An overall summary of adverse events by 2 treatment arms will be performed for induction and consolidation separately. It will include number and percentage of treatment-related AE (TrAE), Grade 3 or higher TrAE, serious TrAE, treatment-related grade 3 or higher AE leading to stop treatment and study discontinuation, death, etc. The worst grade of treatment-related non-hematological AE for each patient will also be summarized by treatment arms for induction and consolidation separately.

The following AEs are considered as hematological AEs:

Anemia, CD4 lymphocytes decreased, Lymphocyte count decreased, Neutrophil count decreased, Platelet count decreased, and White blood cell decreased.

All others that are not in the above list will be classified as Non-hematological AEs.

All collected adverse events are coded in MedDRA version 23.0. The treatment-emergent adverse events (TEAE) are defined as database collected AE that onset on or after the first protocol treatment (Gilteritinib or Midostaurin) date or worsening of a pre-existing AE after treatment. TrAE is defined as the investigators' assessed drug-related adverse events and their causality after drug is administered. All TrAE will be summarized by system organ class and preferred term and 2 treatment arms and displayed in frequency order.

All TrAEs that onset before the first dose of consolidation treatment will be summarized in induction tables. The TrAEs that onset on or after the first dose of consolidation treatment will be summarized in consolidation tables.

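### As worded, the SAP puts consolidation safety summaries on the whole safety population and defines no consolidation-treated set, so consolidation percentages would be understated

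*SAP*

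**What the plan says.** SAP 7.4 defines two analysis populations, safety and efficacy. On the first, SAP 7.4.1 reads: "The safety population is defined as all patients treated with at least one dose of study medication during the study". Membership does not depend on treatment phase.

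SAP 7.5 then applies this population to both phases: "Safety analysis will be assessed by induction and consolidation for the safety population". SAP 7.5.4 repeats the assignment for concomitant medications, "for the safety population for induction and consolidation separately", and the statistic there is a percentage of patients: "the number and percentage of patients taking each medication will be presented by ATC Classification".

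For adverse events, SAP 7.5.6 asks for a summary by arm for each phase: "It will include number and percentage of treatment-related AE (TrAE), Grade 3 or higher TrAE, serious TrAE". It allocates events by onset: "The TrAEs that onset on or after the first dose of consolidation treatment will be summarized in consolidation tables". Earlier events go to the induction tables.

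Not every treated patient reaches consolidation. SAP 4.4.1 says: "Consolidation: There are 0 - 4 cycles of therapy in Consolidation". Protocol 5.2.1 takes patients without CR or CRi off study, and Protocol 12.1 allows consolidation to be skipped: "Patients may proceed to allogeneic transplant after induction or after 0-4 cycles of chemotherapy consolidation".

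**The concern.** A patient who fails induction, dies early or goes directly to transplant has no first consolidation dose. Under the onset rule in SAP 7.5.6 that patient cannot contribute an event to a consolidation table, but does belong to the population named for it. Such patients are structural zeros: they add to the denominator and can never add to the numerator.

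Toxicity of each regimen during induction and consolidation is a secondary objective (Protocol 2.2), and Protocol 12.2.2 promises toxicity frequency tables by phase and arm. A reader of a consolidation table will normally take the percentage as the risk for a patient who receives consolidation. With the literal denominator it is lower than that risk. If the two arms send different shares of patients into consolidation, the comparison of percentages also mixes toxicity with the chance of getting that far.

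**Working it through.** **No plan figure to reproduce.** Neither document gives a consolidation event rate or an expected share starting consolidation. The check is therefore algebra with stated assumptions.

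**Inputs**
- Population: all treated patients (SAP 7.4.1, 7.5, 7.5.4).
- Numerator: events from the first consolidation dose onward (SAP 7.5.6).
- Illustrative arm size: 85, from 170 eligible patients allocated 1:1 (Protocol 12.1). The actual safety population may differ a little.
- Share starting consolidation, *s*: assumed 50% to 80%. The only guide is the CR rate of 50% to 80% that Protocol 1.2 expects with standard induction. It is not a forecast for these arms. Counting CRi could raise the share; direct transplant would lower it.
- True rate among consolidated patients, *r*: assumed 30% for illustration.

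**Formula**

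Displayed rate = events / N(safety) = [events / N(consolidated)] × [N(consolidated) / N(safety)] = *r* × *s*.

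**Dilution within an arm**
- *s* = 50%: 0.30 × 0.50 = 15%.
- *s* = 80%: 0.30 × 0.80 = 24%.
- For true rates of 10% and 50% the displayed ranges are 5% to 8% and 25% to 40%.

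**Comparison between arms, gilteritinib / midostaurin (shares assumed)**

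| Shares | True rates | Displayed rates |
|---|---|---|
| 80% / 80% | 30% / 30% | 24% / 24% |
| 80% / 60% | 30% / 30% | 24% / 18% |
| 60% / 80% | 30% / 30% | 18% / 24% |
| 80% / 60% | 30% / 40% | 24% / 24% |

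Row 1: equal shares dilute both arms but leave their ratio correct. Rows 2 and 3: unequal shares create a 6-point difference where none exists, with a ratio of 0.80/0.60 = 1.33 or 0.60/0.80 = 0.75. Row 4: unequal shares hide a real difference.

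**With a consolidation-treated denominator.** In row 2, 85 × 0.80 = 68 and 85 × 0.60 = 51 patients start consolidation. Expected patients with an event are 68 × 0.30 = 20.4 and 51 × 0.30 = 15.3. Then 20.4/68 = 30% and 15.3/51 = 30%, the true rate in both arms.

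**The case against.** **The denominator is never stated.** The SAP names a population and asks for percentages; it does not use the word denominator. The shells are a separate document approved with the SAP (SAP 2.1 and 10), and the document history for 03 November 2020 records that the phase split was built into them. They may use a consolidation N. This stands: a reader might infer that the final tables will certainly carry the wrong denominator, and the documents do not support that. But where the SAP wants a subset elsewhere it says so. SAP 7.6.5 is limited to FLT3-positive patients given consolidation, and SAP 7.6.8 to CRc patients with MRD evaluated. The safety sections carry no such limit, so a programmer following the text would use all treated patients.

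**Readers could rescale.** SAP 7.5.1 reports disposition, including consolidation, by arm, and SAP 7.5.5 reports cycles received by arm. This largely stands and limits the harm. It does not make the printed percentages right.

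**Bias against gilteritinib is not established.** Because the trial aims to raise CRc with gilteritinib, a reader might infer that its consolidation table will look more toxic. The documents do not support a direction. Additional responders may go directly to transplant, the shares are unknown, and equal shares give no relative distortion.

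**The all-treated denominator answers a real question.** It describes consolidation toxicity as part of the burden of the whole strategy, and it keeps the randomized groups. Patients who start consolidation are selected after randomization by response and transplant choice. This stands, and the fix must disclose it.

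**The induction window.** A reader might also infer that the induction window stays open without limit for patients who never consolidate, and wish to close it 30 days after the last induction dose. Protocol 7.2 already ends routine adverse event follow-up at 30 days, with only related events reported later. A forced closure would lose events. In a one-cycle patient the inhibitor ends about Day 21, so the window would close about Day 21 + 30 = Day 51. Response may be documented up to Day 60 (Protocol 5.2.1), and consolidation generally starts within a month of that (Protocol 5.2.2), so about Day 90. Related events in up to 90 − 51 = 39 days would fall in neither table, contrary to SAP 7.4.1, which includes all safety data to the end of the study.

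**Conclusion.** The point holds on the SAP's wording. The only population named for consolidation safety summaries contains patients who cannot have a consolidation event, and no consolidation-treated set exists. Read literally, dilution is certain once any treated patient skips consolidation and the true rate is above zero. Its size depends on the share starting consolidation: at an assumed 50% to 80%, displayed rates are 0.5 to 0.8 of the true rate. Relative distortion between arms is conditional on unequal shares, and its direction is open.

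The consequence is limited to descriptive safety tables. The primary test, sample size and interim rules are unaffected, and the planned disposition and exposure tables allow partial recovery. The conclusion rests on the SAP text without sight of the shells. It is a cheap improvement.

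**What to change.** In SAP 7.4, add a consolidation safety set: patients in the safety population who received one or more doses of consolidation treatment. In SAP 7.5, 7.5.4, 7.5.6 and 7.5.7, make it the denominator for consolidation adverse event, concomitant medication and laboratory tables, and show its N by arm in each table. Use the same first consolidation dose date to define membership and to assign events to phases. Align the table shells; if they already do this, the SAP need only say so.

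Label between-arm comparisons in this set as descriptive, because it is selected after randomization. That is the small downside.

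Keep the SAP 7.5.6 rule that assigns events to phases, so that every reported event appears in one table, and do not add a 30-day closure of the induction window.

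The cost is one definition, one programming flag and a check of the shells. No new data are needed. SAP 2.1 already provides a running note for updates after finalization.

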### **7.5.1. Disposition**

Disposition data e.g., informed consent, screen failure, randomized, induction patients, consolidation, etc. will be summaries descriptive by treatment arm and overall, for the patients who enrolled into the study. Patients who signed informed consent and randomized are considered as enrolled into the study.

### **7.5.2. Demographics and Baseline Disease Characteristics**

Demographic and baseline disease data, e.g., age, gender, race, WHO classification, disease category, Extra Medullary Disease, baseline blood parameters (including WBC, hemoglobin, platelet, PB blast counts, marrow blast counts, etc), pathology, cytogenetics, ELN risk classification, height, weight etc., will be summarized descriptively (number of patients (frequency), mean, SD, median, minimum, and maximum) by treatment arm and overall, in the analysis population.

Medical history will be summarized by treatment arm and overall, in the safety population.

### **7.5.3. Medical History**

Prior cancer therapy for previous cancer and current cancer, medical history, and signs and symptoms that collected during screening will be summaries by treatment arm and overall.

### **7.5.4. Concomitant Medications and Procedure**

The use of concomitant medications and procedure will be recorded on the CRFs. The concomitant medications will be coded to a World Health Organization Drug Dictionary (WHO-DD) term (Version WHODRUG Version - March 2016).

The use of concomitant medications and procedures will be summarized by arm and overall, for the safety population for induction and consolidation separately. In each of these summary tables, the number and percentage of patients taking each medication will be presented by ATC Classification.

### **7.5.5. Study Treatment Exposure**

A summary of number of induction and consolidation cycles received by treatment arms will be displayed.

### **7.5.6. Adverse Event**

An overall summary of adverse events by 2 treatment arms will be performed for induction and consolidation separately. It will include number and percentage of treatment-related AE (TrAE), Grade 3 or higher TrAE, serious TrAE, treatment-related grade 3 or higher AE leading to stop treatment and study discontinuation, death, etc. The worst grade of treatment-related non-hematological AE for each patient will also be summarized by treatment arms for induction and consolidation separately.

The following AEs are considered as hematological AEs:

Anemia, CD4 lymphocytes decreased, Lymphocyte count decreased, Neutrophil count decreased, Platelet count decreased, and White blood cell decreased.

All others that are not in the above list will be classified as Non-hematological AEs.

All collected adverse events are coded in MedDRA version 23.0. The treatment-emergent adverse events (TEAE) are defined as database collected AE that onset on or after the first protocol treatment (Gilteritinib or Midostaurin) date or worsening of a pre-existing AE after treatment. TrAE is defined as the investigators' assessed drug-related adverse events and their causality after drug is administered. All TrAE will be summarized by system organ class and preferred term and 2 treatment arms and displayed in frequency order.

All TrAEs that onset before the first dose of consolidation treatment will be summarized in induction tables. The TrAEs that onset on or after the first dose of consolidation treatment will be summarized in consolidation tables.

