Second occurrence: Recurrence of the same nonhematological AE or appearance of other new nonhematological AE Grade $\geq$ 3 probably, possibly or definitely due to the study drug (excluding pancreatitis, see below)	Dosing will be interrupted. If the AE resolves to $\leq$ grade 1 within 14 days, the patient may resume dosing at the reduced dose during this or subsequent cycles. If the AE does not resolve to $\leq$ grade 1 within 14 days, the subject will be discontinued from treatment and an end of treatment visit will be performed.
Third occurrence: Recurrence of a prior nonhematological AE or appearance of other new nonhematological AE Grade $\geq$ 3 probably, possibly or definitely due to the study drug (excluding pancreatitis, see below)	The study drug will be discontinued.
At any point, in retrospect, if the investigator determines prior non-hematological Grade $\geq$ 3 AE which was initially attributed as possibly, probably or definitely related to study drug is now deemed unrelated	The study drug will be re-escalated to dose that the participant was on at the time of the AE.
Pancreatitis	Dosing will be interrupted until pancreatitis is resolved, then resume gilteritinib at 80 mg during this or subsequent cycles.
QTcF >500 ms	If the QTcF is >500 ms at any time point, the ECG will be repeated (within 2 hours or as soon as possible). Confirm that potassium and magnesium abnormalities are corrected. A cardiology consult will be obtained as medically indicated. If the repeat ECG confirms a QTcF >500 ms, dosing of study treatment will be interrupted. If QTcF resolves to $\leq$ 480 ms within 14 days from study drug interruption, subsequent dosing will be reduced to 80 mg (or if currently at 80 mg, reduction to 40 mg).
QTc interval increased by >30 msec over screening on ECG on Day 15 of Cycle 1	Confirm with ECG on Day 16. If confirmed, consider dose reduction to 80 mg. If currently at 80 mg, dose reduction to 40 mg.
Posterior Reversible Encephalopathy Syndrome (PRES)	Contact PrECOG, discontinue gilteritinib.

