### 6.1.3 Arm B: Midostaurin

Interrupt midostaurin for Grade 3/4 non-hematologic toxicity thought to be possibly related to midostaurin and restart at same dose when toxicity resolves to  $\leq$  Grade 1. If the toxicity resolves prior to day 21, then restart at same dose to complete current cycle. Missed doses will not be made up.

For QTcF >500, confirmed on repeat study, check potassium and magnesium and correct any abnormalities. If at that time QTcF is >480, restart at 50 mg daily, until QTcF is  $\leq$  480. Once QTcF  $\leq$  480 restart at 50 mg BID.

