## 8 Adverse Event Reporting

### 8.1 Collection of Safety Information

**Adverse Event (AE)** is defined as any new untoward medical occurrence or worsening of a pre-existing medical condition in a patient administered a medicinal product in a clinical investigation and which does not necessarily have a causal relationship with this treatment. An AE can therefore be any unfavorable and unintended sign (e.g., including an abnormal laboratory finding), symptom, or disease temporally associated with the use of a product (investigational or marketed), whether or not considered related to the product (investigational or marketed).

After either informed consent, but prior to initiation of induction, only AEs/SAEs caused by a protocol-mandated intervention not considered standard of care will be collected (e.g., SAEs related to invasive procedures such as biopsies). Please note, if induction is started prior to randomization, AE/SAE collection will start at time of randomization. After the initiation of treatment on-study, any changes from baseline which meet (CTCAE V 5.0) Grade  $\geq 3$  AEs and SAEs must be recorded on the appropriate page of the electronic Case Report Form (eCRF). In addition, AEs less than Grade 3 that meet dose interruption, reduction or discontinuation criteria per Section 6.1 must also be recorded, including:  $\geq$  Grade 2 pancreatitis, QTc interval, PRES, cerebellar toxicity of any grade, creatinine  $>2$  mg/dL and direct or total bilirubin  $\geq 2$  mg/dL. All laboratory results required by protocol (Section 10) will be recorded directly on the laboratory eCRF pages. Per Sections 8.2 to 8.7 additional events will be recorded as AEs and/or SAEs (meeting definitions) on the appropriate eCRF.

If known, the diagnosis of the underlying illness or disorder should be recorded, rather than individual symptoms. The following information should be included for all documented AEs: date of onset and resolution, severity of the event; the investigator's opinion of the relationship to study drug (see definitions below); intervention or treatment required for the AE; action taken with study drug; cause of the event (if known); and information regarding resolution/outcome.

If the Grade  $\geq 3$  laboratory abnormality is a sign of a disease or syndrome (e.g., alkaline phosphatase and bilirubin 5x the ULN associated with cholecystitis), only the diagnosis (e.g., cholecystitis) needs to be recorded on the Adverse Event eCRF.

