As per NCI CTCAE Version 5.0, the term toxicity is defined as adverse events that are classified as either possibly, probably, or definitely related to study treatment. The maximum grade for each type of toxicity will be recorded for each patient, and frequency tables will be reviewed to determine toxicity patterns during induction and consolidation separately by treatment arm.

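### SAP 7.5.6 tabulates treatment-related AEs with no grade limit, but below Grade 3 only selected events are collected, so these rows are not any-grade incidence and may also be unequal between arms

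*SAP*

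**What the plan says.** Analysis. SAP 7.5.6 describes the overall summary by arm, separately for induction and consolidation: "It will include number and percentage of treatment-related AE (TrAE), Grade 3 or higher TrAE, serious TrAE". An unrestricted treatment-related AE (TrAE) row thus sits beside a Grade 3 or higher row. A second table has no grade limit either: "All TrAE will be summarized by system organ class and preferred term and 2 treatment arms and displayed in frequency order". A third reports severity: "The worst grade of treatment-related non-hematological AE for each patient will also be summarized by treatment arms". Protocol 12.2.2 likewise sets no lower grade limit: "The maximum grade for each type of toxicity will be recorded for each patient". SAP Section 8 declares no changes from the protocol analyses.

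Collection. Protocol 8.1 requires Grade 3 or higher AEs and SAEs to be recorded once on-study treatment has begun. Below that grade it says "AEs less than Grade 3 that meet dose interruption, reduction or discontinuation criteria per Section 6.1 must also be recorded", and then names items from Grade 2 pancreatitis upward: "Grade 2 pancreatitis, QTc interval, PRES, cerebellar toxicity of any grade", with creatinine and bilirubin thresholds. Sections 8.2 to 8.7 add special reports, such as liver injury, second cancers, pregnancy and overdose. SAP 6.1 repeats the rule and the list but drops the reference to protocol Section 6.1.

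**The concern.** A TrAE row placed beside a Grade 3 or higher row will be read as any-grade incidence. Ordinary Grade 1 and 2 toxicity need not be recorded in either arm, so the data cannot support that reading. The SAP text does not say so.

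There is a second, less certain issue. If recording below Grade 3 follows the dose-change criteria of protocol 6.1, and those are broader for gilteritinib, the same mild event could count in one arm and not in the other. The events concerned include QT prolongation and pancreatitis, which protocol 11.1 lists among gilteritinib's risks, so readers will look at exactly those rows. Toxicity in each arm is a stated secondary objective (protocol 2.2), and the trial is open-label, so sites know which dose-change section applies.

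**Working it through.** No figure in the plan is in dispute. The check compares texts and then illustrates the size under assumptions.

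**Step 1: what a row without a grade limit contains.** Under protocol 8.1 it holds Grade 3 or higher events, SAEs, lower-grade trigger events and special reports. General Grade 1 and 2 toxicity is absent whichever way the trigger rule is read. This part therefore does not depend on interpretation.

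**Step 2: whether the triggers are the same in both arms.**

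| Criterion | Gilteritinib (protocol 6.1.2) | Midostaurin (protocol 6.1.3) |
|---|---|---|
| Related non-hematologic toxicity | Grade 3 or higher | Grade 3/4 |
| Confirmed QTcF above 500 msec | listed | listed |
| Day 15 QTc rise above 30 msec | listed | not listed |
| Pancreatitis | listed, no grade threshold | not listed |
| PRES | listed | not listed |
| Changes for reasons outside the table, on investigator judgement | stated | not stated |

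The gilteritinib table has the entry "QTc interval increased by >30 msec over screening on ECG on Day 15 of Cycle 1". The midostaurin section opens with "Interrupt midostaurin for Grade 3/4 non-hematologic toxicity thought to be possibly related to midostaurin" and adds only the QTcF rule. Footnote 14 of protocol Section 10 sends a rise above 30 msec to Section 6.1.2 alone. The chemotherapy triggers (cerebellar toxicity, bilirubin, creatinine) apply to both arms.

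Two readings follow:
- If the reference to Section 6.1 governs, pancreatitis, PRES and the Day 15 QTc rise are triggers in Arm A only.
- If the named list governs, it carries no arm label and those items are recordable in both arms.

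The text does not decide between them.

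**Step 3: illustrative size, patient-level TrAE row.** Let g be the share of patients with a Grade 3 or higher TrAE, l the share of the remaining patients who have only lower-grade TrAEs, and c the share of those low-grade-only patients who are captured. All three are assumptions.

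- Recorded rate = g + (1 − g) × l × c
- True any-grade rate = g + (1 − g) × l
- Shortfall = (1 − g) × l × (1 − c)
- Artificial difference with identical true toxicity = (1 − g) × l × (cA − cB)

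Take g from 60% to 90% and l from 30% to 60%:

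- Equal capture, c = 20% in both arms: the difference is 0. The shortfall runs from 0.10 × 0.30 × 0.80 = 2.4 points to 0.40 × 0.60 × 0.80 = 19.2 points.
- Capture 15% versus 0%: the difference runs from 0.10 × 0.30 × 0.15 = 0.45 points to 0.40 × 0.60 × 0.15 = 3.6 points.
- Capture 50% versus 10%: the difference runs from 0.10 × 0.30 × 0.40 = 1.2 points to 0.40 × 0.60 × 0.40 = 9.6 points.

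The first case shows that the row is incomplete even when collection is perfectly balanced.

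**Step 4: a single preferred term.** The 170 eligible patients give 170 / 2 = 85 per arm. Suppose 5% to 25% of each arm had the Day 15 QTc rise and it was recorded as related on gilteritinib only. The row would show 85 × 0.05 = 4.25 to 85 × 0.25 = 21.25, about 4 to 21 patients, against 0. This is an upper illustration on the Arm A-only reading.

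**The case against.** The best counter-argument is that unequal collection is not established. Protocol 8.1 names Grade 2 or higher pancreatitis, QTc interval and PRES outright, with no arm label, and SAP 6.1 repeats the list without pointing to Section 6.1. Footnote 14 applies the mean triplicate QTcF to AE reporting for both drugs. The Day 15 rule needs confirmation on Day 16 and then only asks that a reduction be considered, so it may not be a recording criterion at all. Investigator-judged changes lie, by definition, outside the gilteritinib table. These points stand, and they limit the between-arm part to a possibility.

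Several other points also stand:
- The AE tables are descriptive; no between-arm safety test is planned.
- The SAP never uses the term any-grade.
- ECG values and changes are already summarised by arm (SAP 7.5.9), and laboratory results are summarised by maximum CTCAE grade (SAP 7.5.7). Neither depends on AE triggers.
- The table shells are a separate document and may carry a footnote.
- Restricting the tables departs from protocol 12.2.2, so it is more than a wording change.
- Grade 3 or higher events and SAEs are not perfectly uniform either. Protocol 8.7 defines overdose differently for gilteritinib than for the other drugs, and a symptomatic overdose needs an SAE form.

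None of this makes the ungraded rows an incidence. A footnote alone would leave the tables laid out as an any-grade comparison.

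**Conclusion.** The point holds for completeness: as collected, the TrAE rows without a grade limit and the Grade 1 and 2 cells of the worst-grade table cannot estimate any-grade incidence, and they understate low-grade toxicity in both arms. This rests on the text of protocol 8.1 and SAP 7.5.6 and on no assumed rate.

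Imbalance between arms is possible but not shown. A reader might infer that the collection rule is definitely wider for gilteritinib and will manufacture excess toxicity there. The documents do not support that, because the unlabelled list in protocol 8.1 and SAP 6.1 can equally be read as covering both arms. Nor can the size be derived. The 8.8% with a QTc change above 60 msec in protocol 11.1.9.2 is a maximum change in relapsed or refractory patients, not the Day 15 rise above 30 msec. The figures in the working are illustrations. They suggest that the patient-level row moves little if most patients have a Grade 3 or higher TrAE, and that single preferred terms and the Grade 1 and 2 cells are more exposed.

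**What to change.** - In SAP 7.5.6, base the between-arm overall summary, the system organ class and preferred term table and the worst-grade table on Grade 3 or higher and serious TrAEs.
- Put other events below Grade 3 in a separate table or listing by arm, labelled as selectively collected and not an incidence.
- Enter this in SAP Section 8 as a change from protocol 12.2.2. The running note described in SAP 2.1 is available if the SAP is already approved.
- Reconcile protocol 8.1 and SAP 6.1 on whether the named events below Grade 3 are recorded in both arms, and state the answer beside the listing.
- For QTcF, rely on the by-arm ECG summary already planned in SAP 7.5.9.
- Footnote any overdose reports in the serious row, since their definition differs by drug.

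The cost is SAP and table-shell edits and one Section 8 entry. No collected data are lost. The downside is that there is no any-grade headline percentage. No view is taken on any dose-change rule.
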